10.5.2 Assessment of Study Quality & Exposure to Treatment/Compliance

Study quality will be summarised by arm in terms of withdrawals/losses to follow-up, frequency of deviations and numbers of patients with 0,1,2... deviations, and extent of missing critical data.

Exposure to treatment by arm will be assessed by mean dose/patient and mean planned dose.

10.5.3 Study centre effects

No adjustment will be made for this.

10.5.4 Identification and handling of outliers

For continuous variables potential outliers will be defined as follows (Tukey 1977) after testing for symmetry and if non-symmetric, transforming to approximate symmetry using a “ladder of powers” approach using the Stata command ladder:

“Mild” outliers: $UQ+1.5 \times IQR$ to $UQ+3 \times IQR$ or $LQ-1.5 \times IQR$ to $LQ-3 \times IQR$

Severe outliers: values more extreme than the above

(Note: UQ=Upper Quartile, LQ=Lower Quartile, IQR=Inter Quartile Range)

If after transformation no outliers are apparent then no action will be taken even if values appear as outliers on the original scale, apart from use of the transformation if normality is required for a particular statistical procedure, or to remove the leverage effect of the outlying values.

Otherwise outliers in quantitative data will be queried but no action taken if the result is not amended.

10.5.5 Missing data

No adjustment for missing data will be made for secondary endpoints. If more than 10% of patients have missing baseline or final Ki67 values, then multiple imputation will be attempted for these variables, performing at least 10 separate sets of multiple imputations by treatment arm using chained equations, as implemented in Stata v13 or later. Examples of variables to be included in the imputation process will be baseline and final values of other response variables, and covariates predictive of survival such as age and performance status.

The multiply-imputed data sets can then be recombined for formal analysis, either using the *mim* command prefix or if necessary a bespoke routine to estimate parameter values and combine them using Rubin's rules.

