10.3 Sample Size

In the absence of a clearly defined or a clinically relevant difference for Ki67, the primary efficacy parameter will be the probability that the response in one group will be “better” than the response in the other group. This may be referred to as the Probability of Benefit or PoB, and is directly estimated by the (scaled) Mann-Whitney statistic; in the present context a “good” response is a greater reduction in the Ki67 index in the treated arm, and a useful reduction in Ki67 is taken to be a PoB of 0.67 (odds of 2:1 favouring the intervention, and equivalent to a standardised effect size of 0.62).

To demonstrate a PoB (in terms of a reduced Ki67 index) of 0.67, with 5% two-sided significance and 90% power we require 147 patients (with allocation 3:1 enobosarm: “treatment as usual” control). This can be achieved from a minimum of 7 sites assuming an average of 2 pts/site/month and 2 sites opened/month (actually yielding 150 patients), with duration of accrual of 14 months.

The recruitment rate/site estimate is based on the recruitment to the POETIC study (Smith et al. 2011) from the selected centres. Based on previous studies loss to follow-up is expected to be minimal (<1%) as this is a highly motivated group of participants, follow-up is brief and assessment non-invasive.

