10.5.7 Levels of significance, width of confidence intervals

For analysis of the primary outcome statistical significance will be declared if a two-sided P-value of <0.05 is obtained in favour of enobosarm. All other significance levels will also be 5% two-sided and summary statistics will be presented with 95% confidence intervals. No adjustment will be made for multiple comparisons.

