10.5.8 Analysis of primary and secondary outcomes

The primary analysis will be a Mann-Whitney test comparing the change in Ki67 index from baseline between the two arms. The null hypothesis is that enobosarm is no more effective than standard care alone in terms of reduction in Ki67 score from baseline; that is, the Probability of Benefit is not statistically different from 0.5, while the alternate hypothesis is that addition of enobosarm is superior to standard care alone with a Probability of Benefit of

0.67 or more. Results will be presented in terms of the mean, median and SD of the baseline and final Ki67 scores by arm together with the Mann-Whitney statistic and p-value.

Sensitivity analyses

A sensitivity analysis will be performed with an analysis stratified on baseline Ki67. Similar analyses will be performed on secondary efficacy endpoints.

Tests of assumptions

Like the t-test, the Mann-Whitney test may fail to detect a shift in location if there is also a change in variance, hence as a test of shift in location it assumes equal variance. If the primary analysis or the stratified analysis fails to demonstrate statistical significance then a Beta Regression Model will be fitted that simultaneously estimates changes in mean and location, including terms for baseline and treatment for both mean and scale parameters. If the Beta regression model gives a p value < 0.05 for the treatment effect on the mean then the result will still be declared statistically significant.

For secondary endpoints comparison of change from baseline will be performed by a suitable regression-type model including terms to adjust for baseline and account for differences in variance.

Subgroup analyses

No subgroup analyses are planned.

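### Section 10.5.5 accepts as few as 10 imputations for Ki67, too few to keep a borderline pooled p-value reliably on one side of 0.05

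*Protocol*

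**What the plan says.** - **Trigger.** Protocol section 10.5.5: "If more than 10% of patients have missing baseline or final Ki67 values, then multiple imputation will be attempted for these variables".
- **Number of imputations.** The same section asks for "performing at least 10 separate sets of multiple imputations by treatment arm using chained equations". Ten is a minimum. The section gives no rule for going higher and no criterion for Monte Carlo error.
- **Use of the imputed data.** Section 10.5.5 adds: "The multiply-imputed data sets can then be recombined for formal analysis", with Rubin's rules for combining. Section 10.5.1 allows patients with missing baseline or response data into the intention-to-treat population if their values can be imputed.
- **Analysis and success rule.** Section 10.5.8: "The primary analysis will be a Mann-Whitney test comparing the change in Ki67 index from baseline between the two arms". Section 10.5.7: "statistical significance will be declared if a two-sided P-value of <0.05 is obtained in favour of enobosarm".

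**The concern.** A multiply imputed p-value depends partly on the random draws used to fill the gaps. That part shrinks as the number of imputations, m, grows. Ten is usually enough for efficient estimation, but a success rule with a sharp threshold also needs a p-value that barely moves when the same data are imputed again.

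An analyst who runs exactly 10 imputations complies fully with section 10.5.5. If the result is close to 0.05, whether the pooled Mann-Whitney comparison meets the rule could then turn on the imputation draws and not on the patients' data.

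**Working it through.** **1. The plan's own design figure.** Section 10.3 plans for a Probability of Benefit (PoB) of 0.67, "equivalent to a standardised effect size of 0.62", and states: "with 5% two-sided significance and 90% power we require 147 patients". With 3:1 allocation, the control arm needs (1 + 1/3) × ((1.960 + 1.282)/0.62)² = 36.4 patients, a total of 145.8. Rounding up gives 37 controls and 148 in total; power at 147 is 90.2%. The stated 147 is reproduced. The imputation trigger is therefore more than 14.7 patients, that is 15 or more of 147.

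**2. Monte Carlo error of the pooled test.** Hold the data fixed and let only the imputation draws vary. Scale the total variance with unlimited imputations to 1 and write f for the fraction of missing information. Then:
- the pooled estimate, in z units, varies over seeds with SD √(f/m);
- the between-imputation variance B is estimated as f × χ²(m−1)/(m−1);
- the total variance is T = (1 − f) + (1 + 1/m)B;
- p comes from a t distribution with Barnard-Rubin degrees of freedom (complete-data value 145).

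At m = 10 the seed-to-seed SD of z is √(0.10/10) = 0.10 or √(0.20/10) = 0.14. At m = 100 it is 0.032 or 0.045. A p-value of 0.04 corresponds to z = 2.054 and the threshold to 1.960, a gap of only 0.094. At m = 10 that gap is about one SD or less.

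**3. Results for a limiting p of 0.04** (the p-value with unlimited imputations and a normal reference):

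| Assumed f | m | 95% range of p over seeds | Seeds with p ≥ 0.05 |
|---|---|---|---|
| 0.05 | 10 | 0.030–0.060 | 18% |
| 0.10 | 10 | 0.025–0.071 | 29% |
| 0.20 | 10 | 0.019–0.095 | 40% |
| 0.30 | 10 | 0.015–0.119 | 46% |
| 0.10 | 100 | 0.036–0.049 | 2% |
| 0.20 | 100 | 0.033–0.054 | 10% |
| 0.20 | 200 | 0.036–0.050 | 3% |

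The ranges sit slightly above 0.04 partly because the pooled test uses a t reference and not a normal one. That small shift is not seed variation.

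**4. Other starting points at m = 10.** With a limiting p of 0.03, 6% (f = 0.10) to 19% (f = 0.20) of seeds give 0.05 or more. Results well clear of the threshold are not affected.

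**5. Check by full simulation.** This used 110:37 patients, normal change scores, final Ki67 missing completely at random, imputation by arm, a pooled Mann-Whitney PoB, and 40 seeds of m = 10 per data set.
- Among data sets with limiting p between 0.02 and 0.10, 70–76% (11% missing) and 96–98% (20% missing) gave p-values on both sides of 0.05.
- Over all data sets, with true effects of 0.62 and 0.40, two seeds disagreed on significance in 2.7–5.4% (11% missing) and 6.1–8.0% (20% missing).
- At 11% missing the simulated f was 0.11, so 0.10 is a reasonable value near the trigger.

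**6. Power.** Efficiency relative to unlimited imputations is 1/(1 + f/m). At m = 10 this is 0.990 (f = 0.10) or 0.980 (f = 0.20); at m = 100 it is 0.999 or 0.998. The issue is stability of the p-value, not power.

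**The case against.** The strongest reply is that 10 is only a floor. A team that runs 100 complies, nothing in the protocol contradicts the number, and section 10.5.9 promises a separate analysis plan with more detail. The harm also needs several conditions together: 15 or more patients with missing Ki67, use of the minimum, and a borderline result. Section 10.3 expects under 1% loss to follow-up. Section 7.3.6 protects the tissue by sending a single available research core to the paraffin block. Averaged over all results, two seeds disagree in only a few per cent of data sets.

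Most of this stands and limits the severity. It does not remove the point. The floor is a choice the protocol itself makes, and it is low for a threshold decision. The 1% figure concerns loss to follow-up and does not cover unassessable tissue. Baseline Ki67 relies on tissue left over from the diagnostic core, and section 7.5 has scoring done once all samples are in.

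A reader might infer more than the document supports:
- **That the absence of a seed is a defect.** A seed is ordinary analysis-plan content, and that plan is not shown. A fixed seed would make the result reproducible, though it would not reduce the Monte Carlo error in it.
- **That the seed alone decides the trial's verdict or whether the Beta regression is run.** Section 10.5.8 says: "If the primary analysis or the stratified analysis fails to demonstrate statistical significance then a Beta Regression Model will be fitted". Either analysis can trigger that model, and the model can itself lead to a declaration of significance. A shift in the Mann-Whitney p-value is therefore not decisive alone.
- **That the open-label design makes matters worse.** Ki67 is scored centrally and blinded, and seed variation has nothing to do with who knows the allocation.
- **That the imputed p-value is always the primary one.** Section 10.5.5 says imputation will be attempted and the sets can be recombined; section 10.5.8 does not mention imputation.

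**Conclusion.** The point holds as a minor improvement. The stated minimum of 10 imputations leaves a borderline pooled p-value noticeably dependent on the imputation draws. At a limiting p of 0.04, 29% to 40% of seeds reach 0.05 or more, against 2% to 10% with 100 imputations.

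This rests on an assumed fraction of missing information of 0.10 to 0.20, on the 10% trigger being met, on the minimum being used, and on the pooled result serving as the formal primary analysis. Exposure is confined to limiting p-values of roughly 0.02 to 0.10; towards the ends of that band, few seeds cross the threshold. The finding does not suggest bias, a material loss of power, or an error in the sample size.

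**What to change.** In section 10.5.5, raise the minimum from 10 to 100 imputations. Require the Monte Carlo error of the pooled PoB and of its p-value to be reported. State that the number is increased until the Monte Carlo range of the primary p-value no longer straddles 0.05 or is negligible. The last step matters because 100 does not settle every borderline case: at f = 0.20 and a limiting p of 0.04, about 10% of seeds still reach 0.05 or more, falling to about 3% at 200. The rule should apply equally whichever side of 0.05 the result first falls on. The seed can be set in the statistical analysis plan.

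The cost is a line or two of text and minutes of computing for 147 patients.

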10.5.6 Description of baseline subject characteristics

Categorical baseline variables will be summarised as frequencies and percentages, while continuous variables will be summarised as mean and standard deviation. Variables to be summarise will include baseline values of endpoints together with laboratory values (biochemistry, haematology), demographic and clinical variables.

Patient accrual will be summarised graphically and disposition (ineligibility, losses to follow-up etc.) in a standard CONSORT diagram.

10.5.7 Levels of significance, width of confidence intervals

For analysis of the primary outcome statistical significance will be declared if a two-sided P-value of <0.05 is obtained in favour of enobosarm. All other significance levels will also be 5% two-sided and summary statistics will be presented with 95% confidence intervals. No adjustment will be made for multiple comparisons.

10.5.8 Analysis of primary and secondary outcomes

The primary analysis will be a Mann-Whitney test comparing the change in Ki67 index from baseline between the two arms. The null hypothesis is that enobosarm is no more effective than standard care alone in terms of reduction in Ki67 score from baseline; that is, the Probability of Benefit is not statistically different from 0.5, while the alternate hypothesis is that addition of enobosarm is superior to standard care alone with a Probability of Benefit of

0.67 or more. Results will be presented in terms of the mean, median and SD of the baseline and final Ki67 scores by arm together with the Mann-Whitney statistic and p-value.

Sensitivity analyses

A sensitivity analysis will be performed with an analysis stratified on baseline Ki67. Similar analyses will be performed on secondary efficacy endpoints.

Tests of assumptions

Like the t-test, the Mann-Whitney test may fail to detect a shift in location if there is also a change in variance, hence as a test of shift in location it assumes equal variance. If the primary analysis or the stratified analysis fails to demonstrate statistical significance then a Beta Regression Model will be fitted that simultaneously estimates changes in mean and location, including terms for baseline and treatment for both mean and scale parameters. If the Beta regression model gives a p value < 0.05 for the treatment effect on the mean then the result will still be declared statistically significant.

For secondary endpoints comparison of change from baseline will be performed by a suitable regression-type model including terms to adjust for baseline and account for differences in variance.

Subgroup analyses

No subgroup analyses are planned.

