4.2 Primary Endpoint

Change in the proliferation marker Ki67 (% positive tumour cells) from baseline to after 2 weeks of treatment in the two arms.

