7.3.6 Surgery/Research Core Biopsy

Surgery

The breast surgery will be pre-arranged before the patient begins the enobosarm treatment as part of the patient's standard of care. This visit should be within 24 hours of taking the last dose of enobosarm, this may be the day before surgery or the day of surgery depending on the time the last dose was taken and the time of surgery. Samples taken at surgery should ideally be taken via core biopsy (2 cores) once the tumour has been removed BUT BEFORE the tissue has been placed in formalin.

Research Core Biopsy

Patients who have pre-arranged neoadjuvant chemotherapy or endocrine therapy in place of surgery or before surgery will be required to have an additional core biopsy using a core-cut or tru-cut device under imaging guidance prior to commencement of neoadjuvant chemotherapy/endocrine therapy. All efforts should be made to coincide this biopsy with any planned interventions such as insertion of marker clips (for example to mark tumour site in case of complete pathological response to neoadjuvant chemotherapy). Two cores should be taken (one for an FFPE block and one for the AllProtect sample (see Section 8)). If only one core is available due to the size of the tumour or the patient does not wish to have multiple cores (due to pain at the time of the procedure), the core MUST be used for the FFPE block.

The following samples will be collected for all patients at Visit 2:

- Blood samples
- Core taken and placed in formalin to create an FFPE block (from excised tumour or via research core biopsy)
- Core taken and placed in AllProtect solution (from excised breast tumour tissue or via research core biopsy)

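### The first-line Ki67 test ignores baseline, and baseline adjustment reaches the declared result only through a fallback that gives a second chance at significance

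*Protocol*

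**What the plan says.** The endpoint (section 4.2) is "Change in the proliferation marker Ki67 (% positive tumour cells) from baseline to after 2 weeks of treatment". Section 10.3 sizes the trial on the Probability of Benefit (PoB), estimated by the scaled Mann-Whitney statistic: "a useful reduction in Ki67 is taken to be a PoB of 0.67", described as "equivalent to a standardised effect size of 0.62". It concludes that "with 5% two-sided significance and 90% power we require 147 patients", allocated 3:1.

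Section 10.5.8 then sets out, in order:

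- Primary: "The primary analysis will be a Mann-Whitney test comparing the change in Ki67 index from baseline between the two arms".
- Sensitivity: "A sensitivity analysis will be performed with an analysis stratified on baseline Ki67".
- Fallback: if the primary or the stratified analysis is not significant, a Beta regression is fitted with baseline and treatment terms for both mean and scale. A p-value below 0.05 for treatment on the mean still counts as a significant result.
- Secondary endpoints: change from baseline is compared "by a suitable regression-type model including terms to adjust for baseline and account for differences in variance".

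Section 10.1 describes permuted blocks and names no stratification factor. Section 10.5.7 sets 5% two-sided significance and rules out any adjustment for multiplicity.

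**The concern.** Ki67 is a bounded percentage. On the natural reading, change means the difference in percentage points, though the protocol never says whether it is absolute or relative. On that scale a tumour with a low first reading has little room to fall, and a high first reading tends to come down by itself. An unadjusted ranking of changes treats this baseline-driven spread as noise. With about 37 controls and no stratified randomisation, chance imbalance in baseline also goes uncorrected in the first-line test.

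Two things are at stake. One is efficiency: the information that would sharpen the comparison is already collected. The other is error control: the plan does use that information, but only after a non-significant result, as a second way to succeed.

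**Working it through.** **1. Inputs.** From the protocol: PoB 0.67, standardised effect 0.62, two-sided 5%, 90% power, N = 147, allocation 3:1 (about 110:37). The protocol gives no Ki67 SD and no baseline-final correlation (rho), so these are assumed over ranges.

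**2. The plan's own figure.** PoB converts to a standardised effect by d = √2 × z(0.67) = 0.622, which agrees with 0.62. For two means at 3:1, the control group needs (1.960 + 1.282)² / 0.62² × (1 + 1/3) = 36.4, or 145.8 in total. Noncentral-t power at 110:37 is 0.8999, so 147 reproduces as a t-test sample size. For the Mann-Whitney test, Noether's formula gives N = 10.51 / (12 × 0.75 × 0.25 × 0.17²) = 162, and power of 87.1% at 147. Simulation with normal data gives 88.7%. The planned first-line test therefore has about 87-89% power.

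**3. Adjusted test against change score, normal data, equal SDs.** The variance of a change score is 2σ²(1 − rho). The baseline-adjusted variance is σ²(1 − rho²). Their ratio is (1 + rho)/2, and the effective d is 0.62 / √ratio. At N = 147 the unadjusted change score has 90.2% power by the same formula.

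| rho | variance ratio | adjusted power | N for 90% power |
|---|---|---|---|
| 0.3 | 0.65 | 98.1% | about 96 |
| 0.5 | 0.75 | 96.4% | about 111 |
| 0.7 | 0.85 | 94.2% | about 125 |
| 0.8 | 0.90 | 92.9% | about 133 |
| 0.9 | 0.95 | 91.6% | about 140 |

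The gain runs from about 8 points (rho 0.3) to about 1 point (rho 0.9). With unequal SDs (final/baseline ratio 0.6 to 1.2) the variance ratio was 0.24 to 0.997, so below 1 in every case tried.

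**4. Skewed Ki67 with a proportional effect, 110:37, PoB of absolute change set to about 0.67.**

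- Logit-scale model (median about 15%, between-tumour SD 0.7-0.9, sampling noise SD 0.3-0.5, 2,000 runs each): unadjusted Mann-Whitney 87-90%, van Elteren by baseline tertile 93-96%, rank ANCOVA 95-98%. Type I error of the adjusted tests was 4.6-5.7%.
- A separate simulation at the same allocation and PoB: 86-88% unadjusted, 92-96% for van Elteren or rank ANCOVA, type I error near 5%.
- Log-normal model (median 15%, log-SD 0.6-0.8, rho 0.4-0.8, 3,000 runs each): unadjusted 87-88%, rank ANCOVA 95-99.7%. The highest values occur at low rho. A Mann-Whitney test of log change, with no baseline term, reached 95-97%, so part of the gain here comes from the scale of change. At rho 0.8 it matches rank ANCOVA.

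**5. The rule as written.** If the Mann-Whitney test is not significant, the Beta regression is always fitted. Success is therefore either test at p < 0.05. Assumed model: logit-normal Ki67, logit-SD 0.7, rho 0.4-0.8, 2,000 runs each.

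| | Mann-Whitney alone | Beta regression alone | either |
|---|---|---|---|
| No effect: two-sided rejection | 4.9-5.1% | 6.5-6.9% | 8.3-9.1% |
| Effect present: power | 89-90% | 97-99% | 98-99.5% |

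Other assumed variances gave about 95-97% power and about 8% error for the same rule. Part of the excess comes from the Beta test itself, which runs at 6.5-6.9% under this model; the rest comes from having two chances. These errors count both directions. Section 10.5.7 accepts only results favouring enobosarm, so if errors split evenly the relevant rate is about 4.1-4.6%, against a nominal 2.5%.

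**6. Would changing only the first test be enough?** With van Elteren first (bands cut at 10% and 20%, between-tumour SD 0.8, noise SD 0.4, 2,100 runs) and the Beta fallback kept, power was 97.3% and error 8.3%. With Mann-Whitney first the figures were 97.0% and 8.1%. The fallback must also lose its power to declare success.

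**The case against.** The strongest reply is that the unadjusted test is valid and coherent with the design. The trial is sized on the PoB of the change itself, which the Mann-Whitney statistic estimates directly. Under randomisation, regression to the mean affects both arms alike, and chance imbalance is covered by the 5% error rate. All of that stands. A reader might infer that the first-line test is biased, or that the trial is underpowered because of this choice. Neither is supported: power of the planned test remains about 87-90% at the stated target.

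A reader might also infer that baseline adjustment is confined to a sensitivity analysis and that the power is simply lost. That is wrong too. The Beta regression adjusts for baseline and can decide the result, so the written rule recovers the power. The cost is type I error.

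The size of the gain depends on variances and a correlation that the protocol does not give, and a proportional-effect model favours adjusted tests over absolute change. This also stands, and is why the gain is given as a range.

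Finally, final tissue comes from an excised specimen or, for neoadjuvant patients, who "will be required to have an additional core biopsy using a core-cut or tru-cut device under imaging guidance" (section 7.3.6), from a research core. One might infer that route distorts the comparison. The documents give neither the split between routes nor any effect of route on Ki67, and no calculation here includes it.

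**Conclusion.** The point holds as one of efficiency and error control. The first-line test leaves out a covariate that is already collected. The only route by which baseline affects the declared result is a conditional second test, which takes simulated two-sided type I error to about 8-9%. A single baseline-adjusted test would have about 92-98% power at 147 patients, against about 86-90% unadjusted, with error near 5%. The log-normal model goes higher still at low correlation. With equal SDs and rho of 0.8-0.9 the gain shrinks to about 1-3 points. The direction was the same in every case tried; the size rests on assumed Ki67 variances, correlation and form of effect. The case for removing the second chance does not depend on the gain being large.

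**What to change.** In section 10.5.8, and in the SAP to match:

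- Name one baseline-adjusted test as the sole primary test: either van Elteren on baseline Ki67 bands, or rank ANCOVA on baseline Ki67.
- If bands are used, fix them before any Ki67 result is linked to treatment arm. Section 7.5 has samples scored centrally, blinded, after all have been collected, which leaves time for this.
- Move the unadjusted Mann-Whitney test and the Beta regression to sensitivity analyses, and state that neither can declare significance.
- State whether change is absolute or relative wherever it is still analysed.
- Report the stratum-combined PoB with its 95% CI beside the marginal PoB. The 0.67 in section 10.3 is the marginal quantity, and rank ANCOVA does not itself yield a PoB, so section 10.3 should say which quantity the target refers to.

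Stratifying also by planned tissue route is optional; its benefit has not been quantified.

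The cost is a wording amendment, with no new patients, visits or samples. The stratified PoB is slightly harder to explain, the bands must be chosen in advance, and the sponsor gives up the second route to a significant result.

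### A non-significant Mann-Whitney result can be turned into a significant one by a Beta regression at an unreduced 5% level, so the primary claim does not keep the level set in Protocol 10.5.7

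*Protocol*

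**What the plan says.** Three statements in the Protocol bear on this.

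- **Section 10.5.7, the level.** "For analysis of the primary outcome statistical significance will be declared if a two-sided P-value of <0.05 is obtained in favour of enobosarm". The same section adds: "No adjustment will be made for multiple comparisons".
- **Section 10.5.8, the primary test.** "The primary analysis will be a Mann-Whitney test comparing the change in Ki67 index from baseline between the two arms". The null is a Probability of Benefit of 0.5.
- **Section 10.5.8, Tests of assumptions.** After noting that the Mann-Whitney test can miss a shift in location when the variance also changes, the text continues: "If the primary analysis or the stratified analysis fails to demonstrate statistical significance then a Beta Regression Model will be fitted", "including terms for baseline and treatment for both mean and scale parameters". If the treatment effect on the mean then has p < 0.05, "then the result will still be declared statistically significant".

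The stratified analysis that also appears in the trigger is introduced as a sensitivity analysis: "A sensitivity analysis will be performed with an analysis stratified on baseline Ki67".

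**The concern.** One claim has two routes to significance, each at the full 5%. The second route opens only after the first has failed. It can turn a miss into a success and never the reverse, so it can only add positive results, including false ones.

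The stated motive is unequal variance, but no check of variance opens the second route. A trial with equal variances that simply misses gets the second try too.

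The second test also answers a different question. It concerns a baseline-adjusted mean, whereas the null in 10.5.8 and the sample size in 10.3 are stated as a Probability of Benefit. At stake is whether a declared success on the primary endpoint carries the error rate that the protocol claims for it.

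**Working it through.** **1. The plan's own figures.** Section 10.3 sizes the trial for a Probability of Benefit of 0.67 at 5% two-sided and 90% power, 3:1, N = 147 (about 110 and 37). The standardised effect is √2 × z(0.67) = 0.622, as stated. A two-sample noncentral-t calculation at N = 147 then gives 90.05% power. So the size rests on one test at 5% two-sided.

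**2. Error rate if both tests hold exactly 5%.** Let Z1 and Z2 be the two null test statistics with correlation ρ.

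- Two-sided: 1 − P(|Z1| ≤ 1.96 and |Z2| ≤ 1.96) = 0.05 + 0.05 − P(both reject)
- In favour of enobosarm: 1 − P(Z1 ≤ 1.96 and Z2 ≤ 1.96)

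| ρ | P(both reject) | Two-sided error | In favour |
|---|---|---|---|
| 0 | 0.05² = 0.25% | 1 − 0.95² = 9.75% | 4.9% |
| 0.7 | 1.65% | 10 − 1.65 = 8.4% | 4.2% |
| 0.8 | 2.19% | 10 − 2.19 = 7.8% | 3.9% |
| 0.9 | 2.96% | 10 − 2.96 = 7.0% | 3.5% |
| 0.92 | 3.17% | 10 − 3.17 = 6.8% | 3.4% |

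The level stays at 5% only if the two tests always agree. They cannot, because one ranks change scores and the other models a baseline-adjusted mean.

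**3. Null simulation at 110:37.** The protocol gives no Ki67 distribution, so the following are assumptions: centre about 10 to 18%; baseline-to-final correlation or slope 0.3 to 0.85; logit-normal, Beta or cell-count data. The Mann-Whitney test was run on the change. The Beta regression was fitted to final Ki67 with baseline and treatment in both submodels. Each setting had about 4,000 to 6,000 trials. Selected settings with 4,004 trials each:

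| Setting | MW alone | Beta Wald alone | Either, two-sided | MW in favour | Either, in favour |
|---|---|---|---|---|---|
| Beta data, slope 0.8, precision 15 | 4.6% | 6.3% | 7.6% | 2.1% | 3.0% |
| Beta data, slope 0.8, precision 40 | 4.7% | 6.2% | 7.9% | 2.3% | 3.4% |
| Logit-normal, correlation 0.85 | 5.1% | 7.6% | 9.0% | 2.8% | 4.5% |
| Cell counts, correlation 0.7 | 5.0% | 8.3% | 10.3% | 2.5% | 4.6% |
| Logit-normal, correlation 0.3 | 5.6% | 8.3% | 11.5% | 3.1% | 5.5% |

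Over all settings:

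- The correlation of the two statistics was 0.73 to 0.92.
- Mann-Whitney alone rejected in 4.5 to 5.7%.
- The rule gave 7.6 to 11.7% two-sided with Wald tests and 7.0 to 11.1% with likelihood-ratio tests.
- In favour of enobosarm the rule gave about 3.0 to 5.6%.
- A further simulation at 110:37 gave 7.9 to 9.9% two-sided and 3.3 to 4.8% in favour.

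**4. Where the top of the range comes from.** Two tests that each hold 5% cannot exceed 10% together. Totals above 10% occur only because the Beta Wald test alone rejects in 6.2 to 8.9%, with 37 controls or a distribution that is not Beta. That excess comes from the test, not from the two-try rule.

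**The case against.** **The strongest defence.** The fallback is pre-specified with a stated reason, and the Mann-Whitney p-value must be reported, so a reader would see that success came by the second route. This is a phase II window study, and 10.4 itself says that there is no formal clinical definition of success. This stands as a limit on the consequences. It does not restore the level: pre-specification controls error only if the two tests share the alpha. Having set 5% in 10.5.7 and sized for it in 10.3, the protocol should keep it. Nor is this detail left to the SAP, because the decision rule is fixed here.

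**Stronger readings that a reader might infer, and why they fail:**

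- *The error rate is 8 to 11%.* That range counts both directions, whereas 10.5.7 declares success only in favour of enobosarm. It also depends on assumed distributions and a liberal Wald test. Two-sided rates should be set against 5%, and rates in favour against 2.5%.
- *The fallback drops the direction, so a Ki67 increase would count as success.* The fallback sentence names no direction, but 10.5.7 governs analysis of the primary outcome and 10.5.8 frames the hypothesis as superiority. This is loose wording at most.
- *A miss on the stratified analysis alone gives an extra chance.* If the Mann-Whitney test has already succeeded, the claim is made and the Beta fit adds nothing.
- *Beta regression cannot take a signed change or a zero.* The text does not say that the response is the change. Baseline as a covariate fits a model of final Ki67, and handling of exact zeros is SAP detail.
- *Any positive result would be worthless.* The documents support an inflated error rate, not that conclusion.

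**Conclusion.** The point holds: as written, the primary claim does not keep 5% two-sided, or 2.5% in favour of enobosarm. That follows from the rule itself and needs no assumption about Ki67.

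The size does need assumptions. With both tests at exactly 5% and a correlation of about 0.7 to 0.9, the error is about 7 to 8% two-sided and 3.4 to 4.2% in favour. Under the simulated Ki67 distributions it is about 7 to 11% and 3 to 5.5%, the upper part owing to the Beta Wald test's own excess. In the direction that matters for the claim, the false-positive rate is up to about double its nominal value.

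**What to change.** In 10.5.8, delete the sentence that lets a Beta-regression p-value confer significance. State that the primary conclusion rests on one pre-specified test at 5% two-sided, declared in favour of enobosarm as in 10.5.7. Keep the Beta regression as a supportive analysis, reported whatever the primary p-value. With Mann-Whitney alone the simulated error was 4.5 to 5.7%, which is 5% within simulation noise.

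This takes a short text change and no extra patients or data. The real cost is losing the fallback when enobosarm changes the variance as well as the location.

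If the sponsor wants both routes, split the alpha, for example 0.025 each, and restate the power. As a guide, the noncentrality at 110:37 is 0.622 × √(110 × 37 / 147) = 3.27. By the normal approximation, one test then has power Φ(3.27 − 1.96) = 90% at 0.05 and Φ(3.27 − 2.24) = 85% at 0.025. The power of the pair is at least the latter and would have to be simulated. The split bounds the error at 5% only if each test holds its level. Simulated totals were 4.0 to 6.7%, so the Beta test would also need a better-calibrated p-value than the Wald test gives.
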